- Constitutional syndrome, including but not limited to fever, malaise, unintentional weight loss, night sweat, asthenia, fatigue, loss of appetite.
- New or worsened extremity claudication, bruits and asymmetrical pulses.
- Other features judged by the Investigator to be consistent with a GCA or PMR flare.

The resolution of signs and symptoms of GCA is identified in eCRF “GCA Assessment” page with the question “Based upon the patient’s relevant medical history and the clinical assessment and responses provided above, does the patient have active GCA?” ticked as “No”. The resolution of signs and symptoms of GCA by Week 12 will be determined based on the last non-missing post-baseline GCA assessment measured up to Week 12.

Patients who took rescue CS due to active GCA prior to Week 12 or who permanently withdraw from the study treatment prior to Week 12 will be considered as not achieved disease remission by Week 12.

2. Absence of disease flare from Week 12 through Week 52.

Flare is defined as either 1) recurrence of signs and symptoms attributable to active GCA plus an increase in CS dose due to GCA, or 2) elevation of ESR attributable to active GCA plus an increase in CS dose due to GCA. Increase in CS dose is defined as:

- Any dose increase during the protocol defined steroid taper, or
- Reinitiation of prednisone therapy after the protocol defined taper has been completed.

Patients with disease flare are identified as those with the reason for treatment ticked “rescue therapy” in eCRF “Steroid Medication” page and to the question “If Rescue Therapy, please specify” ticked either “Active GCA” or “Elevated ESR Attributable to Active GCA”.

3. Normalization of CRP (to <10 mg/L, with an absence of successive elevations to ≥10 mg/L) from Week 12 through Week 52

The status of normalization of CRP from Week 12 through Week 52 will be determined based on the CRP values measured at Week 16, Week 20, Week 24, Week 32, Week 40 and Week 52. If there are two or more consecutive visits with CRP ≥10 mg/L, then it is categorized as no normalization of CRP. Intermittent missing CRP at Week 16, Week 20, Week 24, Week 32, Week 40 or Week 52 will be imputed using last value carried forward (LOCF) approach.

4. Successful adherence to the prednisone taper from Week 12 through Week 52

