2.1.3.2 Secondary efficacy endpoint(s)

The following efficacy variables will be assessed:

- Components of sustained remission composite measure at Week 52 and Week 24
- Total cumulative corticosteroid (including prednisone) dose over during the treatment period
- Time to first GCA flare during the treatment period

- GTI Cumulative worsening score (CWS) and Aggregate improvement score (AIS) at Week 52 and Week 24.

Below are descriptions of these variables. Details related to imputation of GTI scores are described in [Section 2.5.2](#).

Components of sustained remission composite measure at Week 52

1. Proportion of patients who achieved disease remission by Week 12.
2. Proportion of patients who have no disease flare from Week 12 through Week 52.
3. Proportion of patients who have normalization of CRP (to <10 mg/L, with an absence of successive elevations to ≥ 10 mg/L) from Week 12 through Week 52.
4. Proportion of patients who successfully adhere to the prednisone taper from Week 12 through Week 52.

Components of sustained remission composite measure at Week 24

1. Proportion of patients who achieved disease remission by Week 12.
2. Proportion of patients who have no disease flare from Week 12 through Week 24.
3. Proportion of patients who have normalization of CRP (to <10 mg/L, with an absence of successive elevations to ≥ 10 mg/L) from Week 12 through Week 24.
4. Proportion of patients who successfully adhere to the prednisone taper from Week 12 through Week 24.

Total cumulative corticosteroid (including prednisone) dose during the treatment period

The total cumulative corticosteroid includes prednisone taper regimen per protocol, use of prednisone (an excess of ≤ 100 mg of prednisone during the study treatment period such as those employed to manage AE not related to GCA is permissible for meeting the definition of maintenance of sustained remission) and rescue corticosteroids dose prescribed for rescue therapy over the treatment period for GCA disease only.

Time to first GCA flare during the treatment period

The duration (in days) from randomization to first GCA flare after clinical remission and up to 52 weeks. Patients who never achieve remission will be censored at randomization day; and those who achieved clinical remission and never flared will be censored at the end of treatment assessment date up to Week 52.

The definition of GCA flare is provide in [Section 2.1.3.1](#) primary efficacy endpoint.

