Clinical remission is defined as resolution of signs and symptoms and normalization of CRP (<10 mg/L). Intermittent missing CRP at visit will be imputed using last value carried forward (LOCF) approach. If missing signs and symptoms, then clinical remission is not achieved.

Glucocorticoid toxicity index (GTI) scores and components

The GTI is intended to capture glucocorticoid (GC)-related morbidity and GC-sparing ability of other therapies (2).

The GTI is composed of two components, the Composite GTI and the Specific List (Table 4). The Composite GTI consists of nine domains (body mass index (BMI), glucose tolerance, blood pressure, Hyperlipidemia, Bone Health (BMD), steroid myopathy, Skin steroid-related Toxicity, Neuropsychiatric - steroid related symptoms and infection) on common steroid-related adverse events anticipated to occur in $\geq 5\%$ of patients treated in a clinical trial involving glucocorticoids. The Specific List consists of 23 items (11 domains) that are mainly less common but serious adverse effects, serving as a complementary tool to the Composite GTI to ensure that all important elements of glucocorticoid toxicity were captured.

The domains of the Composite GTI and the specific list of the GTI will be assessed at baseline, Week 12, Week 24, Week 40 and Week 52, except for bone density (BMD) which will be assessed at Baseline and Week 52 only.

Please note, due to early termination of the study, most patients will not have BMD assessed at Week 52. In addition, for patients who withdraw from the study prior to Week 24, the BMD will not be measured at the EOT visit as no substantial changes are expected within 6 months of treatment. As a result, missing BMD score will be imputed as 'no change'. The BMD measured at the end of treatment (EOT) visit will be included in the definition of cumulative GTI scores (i.e., CWS and AIS as defined below) at Week 52 regardless when the EOT visit is occurred. The BMD domain score will be set to 'no change' in the calculation of the cumulative GTI scores at Week 24.

Scoring of the Glucocorticoid Toxicity Index (GTI)

Domain-specific score for each patient at a visit is defined as the weight assigned based on the change in severity level as described for each domain in Table 4.

Composite GTI score for each patient at a visit is the sum of 9 domain-specific scores at each visit.

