2.4.4.1 Analysis of primary and additional efficacy endpoint(s)

The analysis of primary endpoint of sustained remission at Week 52 will be limited to the cohort of patients who had an opportunity to complete the 52-week treatment period (i.e., Week 52 Analysis set).

The proportion of patients achieving sustained remission at Week 52 will be summarized using counts and percentages by the 4 treatment groups. In addition, the treatment effects between the combined sarilumab (group A+B) group and the combined placebo group (Group C+D) will be compared using a Cochran-Mantel-Haenszel (CMH) test stratified by prednisone dose at baseline (<30 mg/day or ≥30 mg/day).

The additional endpoint of sustained remission at Week 24 will be analyzed in the same fashion in the ITT population.

Sensitivity analysis excluding acute phase reactants:

Sensitivity analysis will be performed for the primary endpoint by removing the acute phase reactants (CRP and ESR) from the definition to mitigate against the possibility of biasing the results due to the known PD effect of sarilumab on acute phase reactants.

Patients achieving sustained remission at Week 52 (or Week 24) excluding acute phase reactants is defined by having met all of the following parameters:

- Achievement of disease remission not later than Week 12. **Disease remission** is defined as resolution of signs and symptoms of GCA.
AND
- Absence of disease flare from Week 12 through Week 52 (or Week 24). **Flare** is defined as recurrence of signs and symptoms attributable to active GCA plus an increase in CS dose due to GCA.
AND
- Successful adherence to the prednisone taper from Week 12 through Week 52 (or Week 24).

The sensitivity analysis will be performed in the same fashion as for the primary endpoint. Descriptive statistics (i.e., counts and percentages) will be provided for the three individual components.

Subgroup analyses:

No subgroup analyses will be performed due to the small sample size.

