Appendix C Summary of statistical analyses

Endpoint	Analysis		Statistical	Supportive	Subgroup	Other
	Population	Primary Analysis	Method	Analysis*	Analysis*	Analyses*
Primary Endpoint						
Patients who achieved sustained remission at Week 52	ITT	Proportion of patients achieving sustained remission at Week 52	CMH test stratified by baseline prednisone dose for combined groups, and descriptive analysis for non-combined groups.	1) Sensitivity analysis;2) Analysis excluding patients who prematurely withdraw from the study due to early termination of the study	No	No
Additional endpoint: Patients who achieved sustained remission at Week 24	ITT	Proportion of patients achieving sustained remission at Week 24	CMH test stratified by baseline prednisone dose for combined groups, and descriptive analysis for non-combined groups	Sensitivity analysis	No	No
Secondary Endpoints						
Patients who achieved of disease remission by Week 12	ITT	Proportion of patients who achieved of disease remission by Week 12	Descriptive	No	No	No
Patients who have absence of disease flare from Week 12 through Week 24 and Week 52	ITT	Proportion of patients who have absence of disease flare from Week 12 through Week 24 and Week 52	Descriptive	No	No	No
Patients who have normalization of CRP (decrease to <10 mg/L) with sustained normalization from Week	ITT	Proportion of patients who have normalization of CRP (decrease to <10 mg/L) with sustained normalization from Week 12 through Week 24 and Week 52	Descriptive	No	No	No

Endpoint	Analysis		Statistical	Supportive	Subgroup	Other
	Population	Primary Analysis	Method	Analysis*	Analysis*	Analyses*
12 through Week 24 and Week 52						
Patients who successfully adhere to the prednisone taper from Week 12 through Week 24 and Week 52	ITT	Proportion of patients who successfully adhere to the prednisone taper from Week 12 through Week 24 and Week 52	Descriptive	No	No	No
Total cumulative prednisone (or equivalent) dose	ITT	Total cumulative prednisone (or equivalent) dose over 52-week treatment period	Descriptive	No	No	No
Time to the first GCA flare after clinical remission up to Week 52	ITT	Time (from randomization) to the first GCA flare after clinical remission up to Week 52	Kaplan-Meier estimates and Cox proportional hazards model for combined groups, and descriptive analysis for non-combined groups.	No	No	No

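### Time to first flare depends on CRP and ESR, which sarilumab lowers, but no hazard ratio without these markers is planned

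*SAP*

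**What the plan says.** SAP 2.1.3.2 defines the endpoint as "The duration (in days) from randomization to first GCA flare after clinical remission and up to 52 weeks". Three rules make it depend on acute phase reactants:

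- **CRP in the remission condition.** "Clinical remission is defined as resolution of signs and symptoms and normalization of CRP (<10 mg/L"). This is SAP 2.1.3.2; it sets no deadline for reaching remission.
- **Day-0 censoring.** "Patients who never achieve remission will be censored at randomization day" (same section).
- **ESR in the flare definition.** The second route to flare in SAP 2.1.3.1 is "elevation of ESR attributable to active GCA plus an increase in CS dose due to GCA". The eCRF Steroid Medication page records it under its own tick box, "Elevated ESR Attributable to Active GCA".

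SAP 2.4.4.1 recognises the problem for another endpoint: "Sensitivity analysis will be performed for the primary endpoint by removing the acute phase reactants (CRP and ESR) from the definition". The stated purpose is to "mitigate against the possibility of biasing the results due to the known PD effect of sarilumab on acute phase reactants". That analysis covers sustained remission at Week 52 and Week 24, with counts and percentages for three marker-free components. Protocol 11.4.2.1 likewise places its sensitivity analyses under the primary endpoint.

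For time to first flare, SAP 2.4.4.2 plans Kaplan-Meier estimates and a Cox model (combined sarilumab versus combined placebo, adjusted for the baseline prednisone stratum) with HR, 95% CI and p-value. The Appendix C row, "Time (from randomization) to the first GCA flare after clinical remission up to Week 52", has 'No' under supportive analysis.

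**The concern.** The SAP accepts that these markers may bias a treatment comparison and guards one endpoint against it. It leaves unguarded a second endpoint that uses the same two markers. Time to first flare is one of the few endpoints reported with an HR, confidence interval and p-value.

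There are two mechanisms.

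1. **CRP condition.** Because sarilumab lowers CRP, the requirement is likely to be easier to meet on sarilumab than on placebo. A placebo patient whose symptoms have resolved but whose CRP stays at or above 10 mg/L does not remit. Day-0 censoring then removes that patient from the risk set altogether, and any later symptomatic relapse is not counted. If persistent CRP marks higher flare risk, this takes higher-risk patients out of placebo and moves the HR up.
2. **ESR route.** Flares attributed to ESR should arise mainly where ESR is not suppressed. They add placebo events and move the HR down.

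What is at stake is whether the HR can be read as prevention of clinical flare.

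**Working it through.** **Plan's own figure.** The documents state no power, event count or HR for time to first flare. The nearest figure is the pooled power in SAP Table 1 (53% of 42 versus 17% of 41). It reproduces with a two-sided pooled-variance chi-square test as 82.3% (alpha 0.01) and 94.5% (alpha 0.05), but it concerns sustained remission at Week 24.

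**Assumptions (none from the documents).** True symptom-flare HR 0.50; follow-up 40 weeks; placebo flare hazard 0.5 to 1.0 per year; a share s of patients in both arms with persistently high-risk CRP biology and twice the flare hazard, who fail the CRP condition on placebo only; ESR-only flares on placebo only, at a fraction e of the symptom-flare hazard. The clock starts at randomization, and no symptom condition is modelled.

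**Arithmetic at time zero.** The sarilumab risk set keeps its high-risk share, so its mean relative hazard is 0.50 × (1 + s). The placebo risk set loses that share and gains ESR flares, so its mean relative hazard is 1 + e. Hence

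HR at time zero = 0.50 × (1 + s) / (1 + e).

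**Over 40 weeks** the high-risk patients flare first, so the Cox estimate falls slightly below the time-zero value when s > 0. Large-sample simulation (ranges are over the placebo hazards):

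| Setting | Time-zero arithmetic | Cox HR over 40 weeks |
|---|---|---|
| e = 25%, s = 0 | 0.50 / 1.25 = 0.40 | 0.40 |
| s = 10%, e = 0 | 0.50 × 1.1 = 0.55 | 0.54 to 0.55 |
| s = 30%, e = 0 | 0.50 × 1.3 = 0.65 | 0.63 to 0.64 |
| s = 10%, e = 25% | 0.55 / 1.25 = 0.44 | 0.43 to 0.44 |
| s = 30%, e = 25% | 0.65 / 1.25 = 0.52 | 0.51 |

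Without the markers the same model gives 0.50 to 0.51 throughout. That agreement is partly built in, because no symptom condition is modelled.

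**Second model.** Replacing the two risk groups with gamma frailty (variance 1, placebo hazard 1.0 per year, one year) gives the same directions. With no true effect, the CRP condition alone gives HR 1.09, 1.20 and 1.36 when 10%, 20% and 29% of placebo are removed. ESR flares alone give 0.94, 0.85 and 0.74 at 10%, 25% and 50% of the symptom-flare hazard. Both together run from 0.80 (10% removed, ESR 50%) to 1.28 (29% removed, ESR 10%).

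**Against sampling error.** The standard error of the log HR is about 2/√d for d flares. Assuming d = 20, the 95% CI multiplies and divides the HR by exp(1.96 × 2/√20) = 2.4; at d = 40 the factor is 1.9. The largest single-effect shift in the table is about 1.25-fold (0.50 to 0.40, or 0.51 to 0.64).

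**The case against.** The case for leaving the plan alone has five parts.

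- **Planned outputs already show something.** SAP 2.4.4.1 gives marker-free component counts, and 2.4.4.2 gives the components with the markers. Comparing them indicates how many patients CRP alone holds back at Week 12 and how many have only ESR-attributed flares after Week 12. This stands. A reader might infer that nothing planned reveals the problem, and that would be wrong. But these are proportions tied to Week 12. They give no HR and do not identify who is censored at day 0.
- **ESR never makes a flare by itself.** A reader might infer that a laboratory value is enough. The definition also requires an increase in corticosteroid dose due to GCA. The Efficacy Assessor, who manages rescue, is normally blinded to ESR and may obtain it only where a medical decision absolutely requires it (protocol 10.1). This stands and should limit ESR-only flares. It does not touch the CRP condition, which is derived at analysis.
- **The CRP hurdle may be low.** Remission can be reached at any of ten post-baseline CRP visits to Week 52, and placebo patients start on prednisone 20 to 60 mg/day. This stands: few patients may be removed.
- **The effects oppose each other and the trial is small.** With 83 patients and nominal p-values (SAP 1.3, 2.4.4.3), the shift may be lost in the confidence interval. This also stands and limits the importance.
- **A marker-free HR is not clean either.** A symptom-only condition still selects patients after randomization, and censoring ESR rescues may be informative because rescued patients cannot return to the taper (protocol 8.2). This stands, so the added HR can only be supportive.

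**Conclusion.** The gap holds, and its importance is modest. The SAP's own reason for removing acute phase reactants applies equally to time to first flare, yet no marker-free HR is planned for it.

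A reader might infer that the HR is biased in sarilumab's favour, or badly biased. The documents support neither: they give no rate of persistent CRP elevation and no rate of ESR-attributed flare, and the two mechanisms pull in opposite directions. Under the assumed rates with a true HR of 0.50, the reported HR is about 0.40 to 0.64 when one effect acts and about 0.43 to 0.51 when both do; at 30% removed plus 25% ESR flares they nearly cancel. These figures illustrate direction and plausible size and are not estimates for this trial. Since all p-values are nominal, the point concerns interpretation of the HR.

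**What to change.** Add to SAP 2.4.4.2 and the Appendix C row a supportive time-to-first-flare analysis:

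- remission is the eCRF active-GCA question answered 'No', without CRP;
- flare is rescue ticked 'Active GCA' only; rescue ticked for elevated ESR is censored at its start;
- same Cox model and baseline prednisone stratum, with the HR reported beside the main one.

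Also report by arm (a) the number censored at day 0 because of CRP alone, that is, with at least one symptom-free post-baseline visit but never meeting clinical remission, and (b) the number of ESR-only flares. These two counts show whether either mechanism was active.

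The cost is one derivation, one model and two counts from data already collected. The text should state that the second HR is supportive and not an unbiased reference, because ESR-rescue censoring may be informative and the symptom-only condition still selects after randomization.

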- a) For worsening score, only the item with the highest weight is scored for any GTI interval (typically three months) with the CWS. As an example, if neither insomnia nor depression were present at the baseline visit but there is now mild Insomnia and moderate depression present at follow-up, then only the moderate depression is scored (+63 points).
- b) For improvement score, improvement as well as worsening can be recorded. Because it is conceivable that one item might improve while another worsens, the item of greatest improvement (highest absolute weight) and the item of greatest worsening (highest weight) are recorded for given GTI interval.

For Infection Domain, the worsening score and improvement score handle the scoring of infections differently, because the CWS and AIS reflect reciprocal measures of GC toxicity.

- a) For worsening score, the most severe infection in every GTI interval is scored.
- b) For improvement score, only the most severe infection occurring over the course of the entire trial is scored.

Step 2: Calculate composite worsening score and improvement score at each visit by summing the 9 domain-specific score.

- a) For composite worsening score, sum the 9 domain-specific worsening scores.

- b) For composite improvement score, sum the 9 domain-specific improvement scores.

Step 3: Calculate cumulative GTI scores by summing composite scores across visits.

- a) For CWS at Week 24, summing composite GTI worsening score at Week 12 and Week 24.
- b) For CWS at Week 52, summing composite GTI worsening score at Week 12, Week 24, Week 40, and Week 52.
- c) For AIS at Week 24, summing composite GTI improvement score at Week 12 and Week 24.
- d) For AIS at Week 52, summing composite GTI improvement score at Week 12, Week 24, Week 40, and Week 52.

Table 4 – The Glucocorticoid Toxicity Index

Composite GTI	Item weight	Specific List¹
1.BMI		
Decrease by \geq 5 BMI units	-36	Major increase in BMI
Decrease by >2 but <5 BMI units	-21	
No significant change (\pm 2 BMI units)	0	
Increase of >2 to <5 BMI units	21	
Increase of 5 or more BMI units	36	
2.Glucose tolerance		
Improvement in HbA1c AND decrease in medication	-44	Diabetic retinopathy
Improvement in HbA1c OR decrease in medication	-32	Diabetic nephropathy
No significant change	0	Diabetic neuropathy
Increase in HbA1c OR increase in medication	32	
Increase in HbA1c AND increase in medication	44	
3.Blood pressure		
Improvement in BP AND decrease in medication	-44	Hypertensive emergency

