Improvement in BP OR decrease in medication	-19	Posterior reversible encephalopathy syndrome
No significant change	0	
Increase in BP OR increase in medication	19	
Increase in BP AND increase in medication	44	
4.Hyperlipidemia		
Decrease in LDL AND decrease in medication	-30	
Decrease in LDL OR decrease in medication	-10	
No significant change	0	
Increase in LDL OR increase in medication	10	
Increase in LDL AND increase in medication	30	
5.Bone Health (BMD)		
Increase in BMD (gain of more than 3%)	-29	Major decrease in bone density
No significant change in BMD (\pm 3%)	0	Insufficiency fracture

Composite GTI	Item weight	Specific List¹
Decrease in BMD (loss of more than 3%)	29	
6.Steroid myopathy		
Moderate weakness to none	-63	Severe steroid myopathy
Moderate to Mild weakness	-54	
Mild weakness to none	-9	
No significant change	0	
None to Mild weakness (without functional limitation)	9	
Mild to Moderate weakness	54	
None to Moderate weakness (with functional limitation)	63	
7.Skin steroid-related Toxicity		
Decrease in Skin Toxicity - Moderate to None	-26	Severe skin toxicity
Decrease in Skin Toxicity - Moderate to Mild	-18	
Decrease in Skin Toxicity - Mild to None	-8	
No significant change	0	
Increase in Skin Toxicity - None to Mild	8	
Increase in Skin Toxicity - Mild to Moderate	18	
Increase in Skin Toxicity - None to Moderate	26	
8.Neuropsychiatric - steroid related symptoms		
Decrease in NP Toxicity - Moderate to None	-74	Psychosis
Decrease in NP Toxicity - Moderate to Mild	-63	GC-induced violence
Decrease in NP Toxicity - Mild to None	-11	Other severe neuropsychiatric symptoms
No significant change	0	
Increase in NP Toxicity - None to Mild	11	
Increase in NP Toxicity - Mild to Moderate	63	
Increase in NP Toxicity - None to Moderate	74	
9.Infection		
No infection	0	Grade IV infection
Oral or vaginal candidiasis or non-complicated zoster (<Grade3)	19	Grade V infection
Grade 3, 4, or 5 infection	93	

¹ Maximum weight is given for specific list events in Blood pressure, Steroid myopathy, Skin toxicity, Neuropsychiatric and Infection domains at each visit. For the rest of domains, specific list events will not affect the corresponding domain specific score.

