Appendix I Baseline glucocorticoid toxicity

Approach to calculating the Baseline glucocorticoid toxicity score: Toxicities assigned weighted scores from the Composite Index to establish a baseline glucocorticoid toxicity score

Toxicity Domain		Points
Body Mass Index (BMI)	BMI < 27	0
	BMI > 27 but < 30	21
	BMI > 30	36
Glucose Metabolism	HgbA1c < 5.7	0
	HgbA1c < 5.7 but on medication	32
	Hgb A1c > 5.7	32
	HgbA1c > 5.7 and on medication	44
	Diabetic retinopathy, nephropathy, or neuropathy (count only one)	44
Lipid Metabolism	LDL < target ^a	0
	LDL < target ^a but on medications	10
	LDL > target ^a on no medications	10
	LDL > target ^a on treatment	30
Bone/Tendon	Normal BMD or no known history of osteoporosis	0
	Osteoporosis	29
	Insufficiency fracture secondary to osteoporosis	29
	Osteonecrosis	29
	Tendon rupture while on corticosteroid	29
Glucocorticoid Myopathy	No myopathy	0
	Minor glucocorticoid myopathy	9
	Moderate glucocorticoid myopathy	63
	Severe glucocorticoid myopathy	63
Skin	No skin toxicity	0
	Minor skin toxicity (one or more than one minor skin item)	8
	Moderate skin toxicity (one or more than one moderate skin item)	26
	Severe skin toxicity (one or more than one moderate skin item)	26
Neuropsychiatric	No neuropsychiatric toxicity	0
	Minor (one or more than one minor NP item: insomnia, mania, depression, cognitive)	11
	Moderate (one or more than one moderate NP item: insomnia, mania, depression, cognitive)	74
	Severe (one or more than one severe NP item: insomnia, mania, depression, cognitive)	74
	Psychosis	74
	Glucocorticoid-induced violence	74
Infection	No GTI-relevant infections within the pre-baseline GTI interval of the study	0
	Oral or vaginal candidiasis or non-complicated zoster (<Grade3) within the pre-baseline GTI interval of the study	19

[figure not shown]
	Grade 3 or Grade 4 infection within the pre-baseline GTI interval of the study	93
Ocular	Increased IOP	33
	Posterior subcapsular cataract	33
	Central serous retinopathy	33
Gastrointestinal	GI perf absence of NSAIDs	33
	PUD without H. pylori	33
Endocrine	Adrenal insufficiency	33

a Target range of <70 mg/dL will be used for LDL domain.

Signature Page

efc15068-16-1-9-sap

Approve & eSign

Approve & eSign

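### The SAP's worked GTI example scores new moderate depression as +63, but the SAP's own scoring rule and Table 4 give +74

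*SAP*

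**What the plan says.** All of the following stands in SAP section 2.1.3.2 unless noted.

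- **General rule** (paragraph on scoring the GTI): a domain-specific score at a visit is "the weight assigned based on the change in severity level as described for each domain in Table 4".
- **Rule for sub-items** (Step 1, Skin and Neuropsychiatric domains): "For worsening score, only the item with the highest weight is scored for any GTI interval".
- **Worked example** (same step): the patient is introduced with the words "if neither insomnia nor depression were present at the baseline visit but there is now mild Insomnia and moderate depression present at follow-up". The score that the SAP gives this patient reads "then only the moderate depression is scored (+63 points".
- **Table 4, domain 8**: the lowest step up is "Increase in NP Toxicity - None to Mild 11"; the next one listed is "Increase in NP Toxicity - Mild to Moderate 63"; and the full step is the row "Increase in NP Toxicity - None to Moderate", with weight 74.
- **Appendix I, baseline toxicity score**: "Moderate (one or more than one moderate NP item: insomnia, mania, depression, cognitive", which carries 74 points.

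The visit scores are summed over Weeks 12 and 24 for CWS at Week 24, and over Weeks 12, 24, 40 and 52 for CWS at Week 52. Section 2.4.4.2 compares CWS between the combined sarilumab and combined placebo groups by ANCOVA, with a 95% CI and p-value.

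**The concern.** The example is the SAP's only numerical illustration of how several items within one domain reduce to a single worsening score, and it sits inside the calculation steps. For the patient it describes, it gives a different number from the table it is meant to apply. Programmers and validators often use such an example as a test case. Code that reads Table 4 correctly would fail this one, and code adjusted to pass it would give too little weight to a new moderate neuropsychiatric toxicity. Two people programming independently could each point to SAP text for a different score. The result feeds an endpoint with a between-group estimate.

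**Working it through.** **Inputs**

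| Item | Baseline | Follow-up | Table 4 weight |
|---|---|---|---|
| Insomnia | none | mild | 11 |
| Depression | none | moderate | 74 |

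For reference, the mild-to-moderate weight is 63.

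**Step 1: apply the SAP's rule.** Neuropsychiatric worsening score = maximum over items of the Table 4 weight for that item's change = max(11, 74) = 74. The SAP prints 63, so its figure is not reproduced.

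**Step 2: look for another route to 63.**
- The mild-to-moderate row gives 63, but the example states that depression was absent at baseline.
- Adding the items gives 11 + 74 = 85.
- Subtracting them gives 74 − 11 = 63, but no rule in the SAP subtracts one item from another.

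**Step 3: is the table or the example in error?** Three checks point to the example.
- Table 4 is additive across levels. Neuropsychiatric: 11 + 63 = 74. Skin: 8 + 18 = 26. Myopathy: 9 + 54 = 63.
- Appendix I gives a moderate neuropsychiatric item 74 points at baseline.
- Protocol section 9.2.1.4 gives 439 as the top of the composite range. The largest Table 4 weights in domain order sum to 36 + 44 + 44 + 30 + 29 + 63 + 26 + 74 + 93 = 439. With 63 as the neuropsychiatric maximum the sum would be 428. Only the upper end serves as a check: the protocol's lower end of −36 is not what Table 4's negative weights would sum to.

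**Step 4: size.** 74 − 63 = 11 points at the visit where the change is scored; 11/74 = 15%.

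**The case against.** The strongest reply is that the SAP already resolves the conflict. The general rule makes Table 4 the source of the weight by change in severity, and the table has a separate none-to-moderate row. A programmer working from these would score 74 and could treat the parenthesis as a slip. The example also exists to show that only the highest-weighted item counts, and that survives: depression is selected over insomnia (11) whether it is worth 63 or 74. This stands, and it makes the shortfall conditional. It does not remove the contradiction.

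A weaker reply is that Table 4's rows are labelled by domain, so a patient with pre-existing mild mania or cognitive impairment would move from mild to moderate and earn 63. The example mentions no such item, and the sub-item rule is written per item, so this does not rescue it.

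A reader might also infer more than the documents support:

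- **The skin domain is affected too.** Using 18 where 26 applies would lose 8 of 26 points, but the SAP prints no skin example and no conflicting skin score.
- **The figure puts CWS on a different scale from its ANCOVA covariate.** ANCOVA does not need a common scale. Appendix I already differs from Table 4: it adds ocular, gastrointestinal and endocrine domains and lists no blood pressure domain. Its 74 is useful only as corroboration.
- **The gap multiplies over visits.** It would reach 22 points at Week 24 (148 against 126) and 44 at Week 52 (296 against 252) only if the same change were scored again at every visit. The SAP describes CWS as adding new toxicities, which does not establish such repeated scoring.

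**Conclusion.** The worked example is wrong as written: under the SAP's own rule the patient scores +74, not +63. The consequence is an understatement of 11 of 74 points (15%) for each none-to-moderate neuropsychiatric change, at the visit where it is scored. It arises only if the program or its validation follows the example in place of Table 4. The documents do not show which was followed, so they do not support a reading that the CWS results are in error.

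The stakes are limited. GTI is a secondary endpoint, the efficacy analyses are descriptive, and all p-values are nominal (SAP 2.4.4 and 2.4.4.3). The classification that splits CWS at zero cannot change, since 63 and 74 are both positive. Any misweighting would apply the same rule in both combined groups, and nothing in the documents indicates a direction of bias. They also give no frequency for none-to-moderate changes, so the effect on group means cannot be estimated. This is a minor consistency correction.

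**What to change.** In SAP 2.1.3.2, Step 1, change the example's score to +74 points (None to Moderate). Beside it, state that the general rule governs, with each item's weight read from Table 4 by its starting and ending level. Check the GTI derivation program and any validation test cases against Table 4, including a none-to-moderate neuropsychiatric case. The cost is one figure, one clause and a short program check; no data collection or analysis method changes.
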